8) Study endpoints

Among 10 stages 3-4 CKD patients with persistent, mild hyperkalemia, we will evaluate, in a quasi-experimental, controlled feeding study, the efficacy of patiomer for maintaining normal serum potassium concentrations when following a plant-rich diet that includes high-potassium fruits and vegetables, as well as the effects of this diet on health outcomes. The participants will be transitioned gradually to a plant-rich diet, as outlined further below.

The interventions will be evaluated primarily in terms of serum potassium concentrations, but health outcomes will also be assessed, including blood pressure, gastrointestinal symptoms, and fasting concentrations of phosphorus, calcium, magnesium, albumin, glucose, insulin, cholesterol, LDL-cholesterol, HDL-cholesterol, triglycerides, urea nitrogen, bicarbonate and C-reactive protein. For all parameters, baseline values will be compared to values at the end of each diet phase (weeks 2 and 4).

9) **Procedures involved**

a. Design.

We will conduct an unblinded, quasi-experimental, controlled feeding study, which will be coordinated through the New York University – Health and Hospitals Corporation Clinical and Translational Science Institute (CTSI). Throughout the study, participants will be prescribed patiromer by the study nephrologist ([name]), which will be administered through the CTSI pharmacy. After a 1-week stabilization period, in which participants are prescribed Patiromer while following their usual diets, the feeding component of the study will occur in two phases. During the first phase (week 2), participants will be transitioned to a plant-rich renal diet, which contains moderate protein (10-15% of kcal), restricts dairy products (≤ 1 serving/day), and eliminates high-potassium fruits and vegetables. During the second phase (weeks 3 and 4), the diet will be altered to provide at-least half of fruits and vegetables from high-potassium sources. To reduce participant burden, meals will be delivered to participants by Portable Chef (New York, NY) three times per week.

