Diets will be designed to match a participant’s estimated energy requirements based on resting energy expenditure (REE) determined by Mifflin St. Joer equation multiplied by 1.4 to account for thermal effect of food, and physical activity. As a precaution, two small snacks (~100 kcal) that are low in potassium will be provided along with meals, and the prescribed research diet will be adjusted on the subsequent delivery, if needed. Participants will be directed to consume the foods provided, and record any deviations from the prescribed diets. As the intent of the study is not to modify fluid or sodium intake, participants will be encouraged to consume water, and use table salt as per their usual practices. Because coffee and tea are high in potassium, participants will be directed to limit their intake to no more than one cup per day.

Research diet prescriptions will be generated by the study coordinator ([name]), and prepared and delivered to participants by Portable Chef, a commercial kitchen located in Manhattan that specializes in providing catered meal plans. Meals will be prepared from scratch, using a commercial food scale (TE10FT, Taylor Precision Products, Inc., Oak Brook, IL). Any food items that may undergo commercial processing (e.g., enriched meats) will be carefully selected to ensure that they contain no added sodium, phosphorus or potassium. To ensure the

privacy of participants, staff at Portable Chef will not be provided any participant information, apart from their name, address and phone number, which are necessary to coordinate meal deliveries.

Table 3. Dietary guidelines for research diets

Food Group	Low-K Plant-rich Diet	Liberalized Plant-Rich Diet
Protein Foods	• ¼ animal, ¾ plant	• ¼ animal, ¾ plant
Grain Products	• ½ refined, ½ whole grain	• ½ refined, ½ whole grain
Dairy Foods	• ≤1 serving/day	• ≤1 serving/day
Fruits & Vegetables	• Low-K only	• ½ low-K, ½ high-K

K, potassium

b. Measures. Unless otherwise noted, measurements occur at baseline, and at the end of phase I (week 1) and phase II (week 3). With the exceptions of patiromer dose (obtained from the CTSI Pharmacy) and data obtained from the participant’s medical charts, study measurements will be obtained during visits to the CTSI Clinical Research Center (CRC) at Bellevue Hospital. A summary of study visits and procedures is provided at the bottom of this section (Table 4).

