A descriptive analysis of all data collected will be performed using appropriate graphical and numerical exploratory data techniques. The information obtained from this preliminary investigation of the data will be used to: (1) assess data quality and completeness, (2) describe univariate distributions at baseline and follow up, and (3) create summary statistical data for outcome variables at each time point, including the proportion of participants with hyperkalemia. We will identify features of the data that may necessitate special analytic methods (e.g., excess zeros, missing data, departures from distributional assumptions, outliers).

For analytic analyses, we will examine: (1) changes in outcome variables (blood pressure, gastrointestinal symptoms, and fasting concentrations of potassium, phosphorus, calcium, magnesium, albumin, glucose, insulin, cholesterol, LDL-cholesterol, HDL-cholesterol, triglycerides, urea nitrogen, bicarbonate and C-reactive protein), and covariates (weight, medications, dose of Patiromer) between baseline and the end of each diet phase, and (2) relationships between the changes in outcome variables and covariates. Changes in study outcomes will be graphically depicted using means \pm SD or median (IQR) as measures of central tendency and variance. Changes in study outcomes will be analyzed using repeated-measures analysis of variance with post-hoc Tukey HSD test. Because of the small sample size, covariates will be reported instead of being included in a multivariable model. Depending on the types of covariate and outcome of interest, subgroup analyses may be performed with these participants removed from the dataset. For example, if a participant's dose of phosphorus binder medications changed during the study, the analysis of phosphorus concentrations would be conducted with/without this participant. Given the short duration of this study (4 weeks) in relation to typical monitoring of patients with stage 3B-4 CKD, we expect that that few, if any, subgroup analyses will be required.

12) Provisions to Monitor the Data to Ensure the Safety of Subjects

Protection against Risk.

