Prior to the intervention, participants will receive education on the signs and symptoms of hyperkalemia; muscle weakness, abnormally slow or rapid heart rate, and heart palpitations (from Patient education: Hyperkalemia (the basics); UpToDate.com)⁶. Participants will be directed to monitor themselves for these conditions, and to go to the emergency room if they start experiencing them, making sure to notify the emergency department staff about their participation in the study. Standard treatment for acute episodes of hyperkalemia includes intravenous infusions of calcium gluconate and glucose/insulin, often followed by polystyrene sulfonate or emergent dialysis to remove excess potassium. The emergent treatment of adverse events will be at the discretion of the attending physician. In the event of any admission to the emergency room (even if determined to be unrelated to hyperkalemia), participants will be asked to alert the study PIs as soon as possible.

The intervention contains several features to lower the risk of hyperkalemia. For one, the research diets will be prepared for participants to provide control over the dietary potassium exposure. We will use the feeding study approach that gradually increases dietary potassium in a step-wise manner in order to prevent large shifts in dietary potassium intake. During phase I, participants will be stabilized on a plant-rich diet that restricts dairy products and excludes fruits and vegetables that are high in potassium. This closely approximates the current dietary recommendations for CKD patients with hyperkalemia, but does include plant-based foods from the Protein Foods Group (legumes, nuts, seeds), which are high in potassium (>200 mg/serving). However, compared to the typical Western diet, plant-rich diets are more alkaline, and are higher in fiber, factors that are thought to help control serum potassium concentrations⁴. After a week of consuming this diet, high-potassium fruits and vegetables will be introduced, and make up half of the fruit and vegetable servings. We will closely monitor participants’ adherence to the research diets through daily food records to ascertain their adherence with the study diets – participants that are determined to be non-adherent with the research diets at the end of phase I (defined in section 14) will be withdrawn from the study.

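### Tukey HSD adds a formal week 4 versus week 2 test that the plan does not ask for and that, for blood pressure, the 13 analytes and gastrointestinal symptoms, cannot be separated from time on the shared diet and on patiromer

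*Combined protocol and SAP*

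**What the plan says.** **Design.** Section 9.a describes the trial this way: "We will conduct an unblinded, quasi-experimental, controlled feeding study". There is one group. Week 1 is patiromer on the usual diet. Then "During the first phase (week 2), participants will be transitioned to a plant-rich renal diet", and after that "During the second phase (weeks 3 and 4), the diet will be altered to provide at-least half of fruits and vegetables from high-potassium sources". Section 12 confirms the order and the length of the first step: "After a week of consuming this diet, high-potassium fruits and vegetables will be introduced, and make up half of the fruit and vegetable servings".

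**Diets.** Table 3 sets four food-group rules. Three are the same in both diets: protein ("¼ animal, ¾ plant"), grains ("½ refined, ½ whole grain") and dairy (at most one serving a day). Only the fruit and vegetable rule changes.

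**Measurements.** In Table 4, blood pressure and the 13 non-potassium analytes are read at baseline, week 2 and week 4. Gastrointestinal symptoms are read at those visits and also at week 1. Potassium is read at screening and every week.

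**Comparisons.** Section 8 says that for all parameters "baseline values will be compared to values at the end of each diet phase (weeks 2 and 4". Section 11 likewise examines changes between baseline and the end of each phase, and then names the method: "Changes in study outcomes will be analyzed using repeated-measures analysis of variance with post-hoc Tukey HSD test". Covariates, including patiromer dose, are reported and not modelled.

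**The concern.** Tukey HSD is an all-pairs procedure. With three visits it tests three pairs: baseline versus week 2, baseline versus week 4, and week 4 versus week 2. The plan states a purpose for the first two only.

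The third pair has no clean interpretation here. Between weeks 2 and 4 three things change together: the produce rule, the time spent on the shared protein, grain and dairy rules, and the time on patiromer, whose dose is reviewed weekly. With one fixed order and no control group, the data cannot separate them. Because the two visits are labelled as the ends of two named diets, a significant week 4 versus week 2 result could easily be taken as the effect of high-potassium produce.

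Carrying the third pair also widens the intervals for the two comparisons the plan does want, in a trial of 10 people.

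**Working it through.** The documents give no power calculation, effect size or SD for these outcomes, so there is no figure of the plan's to reproduce.

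**1. Exposure at each reading** (sections 9.a and 12)

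| Reading | Weeks on shared diet rules | Weeks on patiromer | High-potassium produce |
|---|---|---|---|
| Baseline | 0 | 0 | no study diet |
| Week 2 | 1 | 2 | none |
| Week 4 | 3 | 4 | half of fruit and vegetables, 2 weeks |

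Week 4 minus week 2 therefore carries 3 − 1 = 2 more weeks of shared diet and 4 − 2 = 2 more weeks of patiromer, together with the produce change. The introduction to section 9.b labels the phase ends as weeks 1 and 3; counted from the start of feeding, this gives the same 1 and 3 weeks.

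**2. How much could time alone produce?** Assumptions: high-potassium produce has no effect, and the shared-diet effect approaches a plateau with half-life h days. The share reached after t days is f(t) = 1 − 0.5^(t/h).

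| h (days) | f(7), week 2 | f(21), week 4 | Difference |
|---|---|---|---|
| 3 | 0.80 | 0.99 | 0.19 |
| 7 | 0.50 | 0.875 | 0.375 |
| 14 | 0.29 | 0.65 | 0.35 |

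So 19% to 38% of the plateau effect appears as a week 2 to week 4 change. For much faster responses it all but vanishes: with an exponential time constant of 0.25 weeks it is 2%.

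**3. How often would Tukey flag the pair?** Simulation of 60,000 trials per setting, n = 10, three visits, compound symmetry, within-person residual SD = 1. A flag means |mean(week 4) − mean(week 2)| > q × √(MSE/10), with q(0.95; 3, 18) = 3.609. The error degrees of freedom are (10 − 1) × (3 − 1) = 18.

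| Plateau effect | h = 3 | h = 7 | h = 14 |
|---|---|---|---|
| 0 | 2% | 2% | 2% |
| 0.5 SD | 2% | 3% | 3% |
| 1 SD | 3% | 6% | 6% |
| 2 SD | 6% | 22% | 19% |

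**4. What the extra pair costs**

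- Tukey critical value: 3.609/√2 = 2.552.
- Two-sided Dunnett, two contrasts, correlation 0.5, 18 df: 2.40 (2.401 by simulation).
- Interval half-width in residual SDs is the critical value × √(2/10), and √0.2 = 0.447. Tukey: 2.552 × 0.447 = 1.14. Dunnett: 2.401 × 0.447 = 1.07.
- Ratio: 2.401/2.552 = 0.94, so intervals are about 6% narrower.
- Equivalent sample size: 10 × (2.552/2.401)² = 11.3.

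These figures are for the outcomes read at three visits. They do not carry over unchanged to gastrointestinal symptoms if the week 1 reading is included in the model.

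**The case against.** The strongest reply is that the plan never draws the faulty conclusion. A reader might infer from the two named diets, the phase labels and the Tukey test that the plan credits the week 2 to week 4 change to high-potassium produce. The documents do not support that. Section 8 sets the target as the effect of the plant-rich diet including that produce, as a whole. Section 12 explains the steps as a safety measure. Section 15 mentions the need to limit high-potassium plant foods separately from the benefits of a plant-rich pattern, and the former fits the primary potassium outcome. This objection stands: the fault is an unrequested test without a stated interpretation, not a false claim.

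A reader might also infer that the confounding always favours the liberalized diet. That does not follow either. Patiromer runs throughout, and section 12 lists hypomagnesemia in 5.3% of treated patients; a magnesium fall continuing after week 2 would count against that diet.

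Third, the higher flag rates need a large effect. At 0.5 SD they hardly differ from the null, and the documents give neither response times nor SDs. This stands as well.

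Last, Tukey is a valid procedure and the precision gain is small. That is true, but the pair given up is one the plan never requested and could not interpret.

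**Conclusion.** The point holds in a limited form. It is certain from the documents that the phases last one and two weeks in fixed order, that three of the four diet rules are shared, and that Tukey HSD tests a pair outside the comparisons named in sections 8 and 11. For blood pressure, the 13 analytes and gastrointestinal symptoms, that pair is confounded with two more weeks of shared diet and of patiromer.

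How far this could mislead, and in which direction, is not known. The ranges in the working rest on an assumed exponential response, no produce effect, and plateau effects of 0.5 to 2 residual SD. The precision gain of about 6% needs none of these, only the three-visit model with compound symmetry.

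Severity: minor. These are secondary outcomes of a proof-of-concept study, and the potassium comparisons are not affected by this point.

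**What to change.** 1. In section 11, for outcomes analysed by repeated-measures ANOVA at baseline, week 2 and week 4, replace Tukey HSD with Dunnett-type comparisons of week 2 and week 4 against baseline. If gastrointestinal symptoms are modelled with their week 1 reading, state which baseline contrasts are tested and set the critical value for that number.
2. Report week 4 minus week 2 for these outcomes, including gastrointestinal symptoms, only as a descriptive estimate. State that it is confounded with 3 versus 1 weeks on the shared diet and 4 versus 2 weeks on patiromer, and that it will not be attributed to high-potassium produce.
3. In sections 8 and 11, describe baseline versus week 4 as the effect of the whole package: plant-rich diet, patiromer and time. It is not the effect of diet alone, because patiromer starts in week 1 and blood pressure and the analytes are not read again before feeding begins.

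The cost is a few sentences in two sections and a different post-hoc option; no visit, sample or treatment changes. The downside is that no formal test of a separate produce effect on these secondary outcomes is made.

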6) Study-Wide Recruitment Methods

Potential participants will be identified using two recruitment methods: 1. Referral by the patient's nephrologist, and 2. DataCore directed search of electronic medical records. Nephrologist referral patients will be obtained from the New York Harbor VA Healthcare System, NYU Langone Health, and Bellevue Hospital. The DataCore directed search of electronic medical records will be limited to patients of nephrologists in the Division of Nephrology who have an episode of mild hyperkalemia in the past 6-months. Once identified using the electronic medical record search, the patient's nephrologists will be notified about their potential eligibility. Per the study inclusion criteria, nephrologists will be asked to confirm that the patient is appropriate for the study.

- (a) [name] or [name] will review each section of the written consent form with the referred participant, ask the participant if they understand each section, and clarify any questions they may have. The participant and the person obtaining consent will sign and date the consent form. Copies of the consent, which includes the contact information of the PI ([name]), will be provided to the participant and sent to the patient's nephrologist. Informed consent will be considered an ongoing process throughout the study, and participants' questions regarding their rights and responsibilities will be addressed whenever they occur.
- (b) Once enrolled, [name] and [name] will meet to verify that the participant meets the inclusion/exclusion criteria. This information will be obtained from the patient's electronic medical record.
- (c) Study staff will contact eligible patients, and schedule a fasting screening appointment (at least 8 hours of fasting).

A fasting blood sample will be obtained at the screening visit, and analyzed for potassium. If this test is in the range of mild hyperkalemia (potassium 5.1 to <6.5 mEq/L), the participant will be deemed to have persistent hyperkalemia, and be accrued. Otherwise they will be deemed ineligible, and excluded from the study. Regardless of enrollment status, all eligible patients who are invited to participate in the study will be reimbursed \$25.00 for time and travel expenses incurred by attending the screening visit.

7) Study Timelines

We will recruit 10 participants. Given the intensiveness of the intervention, no more than two participants will be enrolled in the intervention at a time.

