i. Patiromer. Patiromer dosing will be determined based on fasting potassium concentrations measured at the end of each week, factoring in both the absolute concentration, as well as the rate of change. The baseline dose of patiromer will correspond to the study by Weir et al. (2015); 8.4-g once per day for participants with a baseline serum potassium of ≥ 5.1 mEq/L. The following dosing schedule (Table 2) will be used for managing hyperkalemia during the study:

Table 2. Dosing of patiromer during the study based on serum potassium concentrations

Potassium	Change in Potassium	Action
<3.8 mEq/L	Same or decreased	Contact study nephrologist to determine dose
<3.8 mEq/L	Increased	Continue with current dose
3.8-5.0 mEq/L	Changed <0.5 mEq/L	Continue with current dose
3.8-5.0 mEq/L	Changed ≥ 0.5 mEq/L	Continue with current dose, but notify study nephrologist
5.1-6.0 mEq/L	Decreased	Continue with current dose
5.1-6.0 mEq/L	Same or increased	Contact study nephrologist to determine dose
>6.0 mEq/L	Decreased	Continue with current dose, but notify study nephrologist
>6.0 mEq/L	Same or increased	Contact study nephrologist to determine dose

ii. Research Diets. The guidelines for research diets are outlined in Table 3. With the exception of the Dairy Food Group, diets will be balanced according to the USDA MyPlate. Diets will be based on a 7-day menu cycle, and will be reviewed by participants during the screening visit. In order to promote participant adherence with the diets, participants will be permitted to select appropriate substitutes based on their food preferences from a list of pre-approved substitutes. For example, if a participant does not like to eat apples, they may substitute this for a list of other low-potassium fruits.

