iii. Serum potassium concentrations. The primary purpose of this study is to evaluate the efficacy of patiromer for maintaining serum potassium concentrations in CKD patients during transition to a liberalized plant-rich diet by comparing fasting serum potassium concentrations at screening to values at the end of phase I (week 2) and phase II (week 4) of the study. However, because potassium concentrations are also being used to titrate the dose of patiromer needed to achieve normal potassium concentrations, fasting serum potassium concentrations will also be measured at the end of weeks 1 and 3. To ensure a rapid response to changes in serum potassium concentrations, blood samples obtained at the CTSI CRC will be immediately delivered to the study laboratory at Tisch Hospital for analysis, and the results sent to the CTSI Pharmacy for evaluation (section 10.a.i.). Participants will be directed to pick up new prescriptions from the CTSI Pharmacy on the days of measurement. To obtain a measurement of serum potassium concentration, a 0.5 mL sample of blood is required.

iv. Blood pressure. Systolic and diastolic blood pressures will be measured after 5-minutes of rest in a seated position with their arm supported at the level of their heart and their feet resting on the floor using an automatic sphygmomanometer. Blood pressure measurements will be obtained in duplicate with a third measure obtained if the systolic or diastolic values on repeated measurement differ by more than 5 mmHg.

v. Gastrointestinal symptoms. The frequency and severity of participant gastrointestinal symptoms in the previous week (abdominal cramping, abdominal discomfort, indigestion, infrequent or difficult to pass bowel movements, flatulence, loose or watery stools) will be self-reported via an investigator-developed questionnaire at baseline, and at the end of the stabilization period (week 1), phase I diet (week 2), and phase II diet (week 4).

vi. Other biochemical parameters. Fasting blood samples will be obtained at the CTSI CRC, and analyzed for concentrations of phosphorus, calcium, magnesium, albumin, glucose, insulin, cholesterol, LDL-cholesterol, HDL-cholesterol, triglycerides, urea nitrogen, bicarbonate and C-reactive protein. Similar to serum potassium concentrations, blood samples will be delivered by study staff to the laboratory at Tisch Hospital for analysis. To obtain these biochemical measurements, approximately 5.0 mL of blood is required.

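### Table 2 requires no notice to the study nephrologist when potassium is still below 3.8 mEq/L but has risen, however small the rise and however low the value

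*Combined protocol and SAP*

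**What the plan says.** Section 9, a.i bases weekly dosing on fasting potassium, "factoring in both the absolute concentration, as well as the rate of change". Table 2 turns this into eight rows. Those that matter here are:

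- Below 3.8, flat or falling: "Same or decreased Contact study nephrologist to determine dose".
- Below 3.8, rising: "<3.8 mEq/L Increased Continue with current dose".
- 3.8 to 5.0, changed by 0.5 or more in either direction: "Continue with current dose, but notify study nephrologist". A change of less than 0.5 in this band carries no notice.
- 5.1 to 6.0, falling: continue, no notice.
- Above 6.0, falling: continue, with notice to the nephrologist.

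The table does not say what change is measured from.

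On entry, Section 6 accrues a participant on the screening sample: "If this test is in the range of mild hyperkalemia (potassium 5.1 to <6.5 mEq/L". On timing, week 2 and week 4 values serve the main comparison, and Section 9, b.iii adds that "fasting serum potassium concentrations will also be measured at the end of weeks 1 and 3". The same section sends results to the research pharmacy for evaluation.

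**The concern.** A potassium below 3.8 that is flat or falling goes to the nephrologist, who sets the dose. The next weekly value shows whether that decision was enough. If it is 0.1 higher but still below the 3.8 to 5.0 band, the table asks for nothing beyond continuing the binder. Any rise, however small, removes the duty to report, and there is no lower limit at which the duty returns.

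Elsewhere the table does ask for notice when a value is moving the right way: a falling value above 6.0, and a return to 3.8 to 5.0 by a step of 0.5 or more. What is at stake is a small point of participant safety, namely whether the clinician who chose the dose must be told that potassium is still low. No endpoint or analysis depends on it.

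**Working it through.** **Inputs.** Table 2 rows as above; screening potassium 5.1 to below 6.5 (Section 6); withdrawal at 6.5 or above (Section 4); potassium at the end of weeks 1 to 4 (Section 9, b.iii and Table 4). I assume results to one decimal place, as the table's bands imply. Each week's value is compared with the one before, and week 1 with screening.

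**1. When can the row apply?** If change is measured from screening (5.1 or higher), a value below 3.8 is always a decrease and the row can never apply. The previous weekly value is the only natural reading that gives the row a use.

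**2. Has the nephrologist already been contacted?** The first value below 3.8 in any run follows a value of 3.8 or higher, so it is a fall and triggers contact. A value in the rising row must follow a lower value, which is itself below 3.8. Contact has therefore always happened earlier in the same run. As a check, take screening at 5.1 to 6.4 (14 values) and each of weeks 1 to 3 at 2.5 to 6.4 (40 values; the floor of 2.5 is assumed):

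- Rising pairs that stay below 3.8, from 2.5 to 3.7 (13 values): 13 × 12 / 2 = 78.
- Entries to the row at week 1: 0. At week 2: 14 × 78 × 40 = 43,680. At week 3: 14 × 40 × 78 = 43,680.
- Entries without earlier contact in the same run: 0.

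These are unweighted logic counts, not frequencies.

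**3. What does the table do with particular moves?**

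| Move (mEq/L) | Action |
|---|---|
| 3.0 to 3.1 | continue, no notice |
| 3.2 to 3.7 (rise 0.5, still low) | continue, no notice |
| 3.3 to 3.8 (rise 0.5, back in band) | continue, notify |
| 3.6 to 4.0 (rise 0.4, back in band) | continue, no notice |
| 6.4 to 6.2 | continue, notify |

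**4. How far must potassium fall?** A value of 3.7 cannot rise by 0.1 and remain below 3.8, so the preceding value must be 3.6 or less.

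- One dosing decision in the row: 5.1 − 3.6 = 1.5, reached by week 2 at the latest (3.6 at week 2, then 3.7 at week 3).
- Two decisions: week 1 at 3.5 or less, then for example 3.6 and 3.7; 5.1 − 3.5 = 1.6, by week 1.

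Higher screening values need larger falls.

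**5. Ceilings.** On-study dosing decisions follow weeks 1, 2 and 3; the row is impossible at week 1, so at most 2 of the 3 fall in it, or 2 × 10 = 20 over ten participants. Counting week 4 as well, at most 3 values per participant could generate a notice, or 3 × 10 = 30. Both ceilings require every participant to fall steeply by week 1 and then creep upward while staying low.

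**6. Does any other section cover it?** The contact and repeat-test rules in Section 12 concern abnormally high values or values climbing fast towards hyperkalemia. The mid-study review in Section 12 looks for moderate-severe hyperkalemia and protocol issues. Potassium-based withdrawal is at 6.5 or above only. None requires a persisting low value to be passed on.

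**The case against.** The strongest reply is that the table is consistent on its own terms: out of range and not improving means contact, out of range and improving means continue. The adjacent row on the high side, 5.1 to 6.0 and falling, is equally silent. The 3.8 to 5.0 row flags rapid change rather than recovery, since a return to band by less than 0.5 is also silent. This stands, and it weakens any charge of general asymmetry. What remains is that the high side has a further tier above 6.0 where even an improving value is notified. The low side has no such tier, so a move from 2.5 to 2.6 is treated like one from 3.6 to 3.7.

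A second reply is that the nephrologist is unlikely to be unaware: "Throughout the study, participants will be prescribed patiromer by the study nephrologist", and "Participants will be directed to pick up new prescriptions from the CTSI Pharmacy on the days of measurement". Section 21 gives the principal investigator, a nephrologist, oversight of safety and patiromer prescriptions, and no more than two participants are on the intervention at a time. This also stands as to likelihood, but none of these provisions requires the result to be relayed.

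A third reply is that the table exists to manage hyperkalemia, that no section defines a value below 3.8 as harmful, and that the adverse reactions listed for patiromer do not include hypokalemia. That is fair, and it limits the severity. Yet the table itself treats a flat or falling value below 3.8 as needing a physician's decision.

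A reader might infer that low potassium goes unmanaged, or that a participant could be kept on a binder without the nephrologist ever having been involved. The documents do not support that: every entry to this row follows a mandatory contact, and any later flat or lower value below 3.8 triggers another.

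**Conclusion.** The point holds as a minor gap in a safety rule. Read literally, Table 2 continues the binder at a potassium still below 3.8 with no required notice, whatever the size of the rise, and no other section supplies the notice. What is missing is repeat notification, not first contact.

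This rests on change being measured from the previous weekly value; if it is from screening, the row is empty and the gap disappears. The documents give no frequency for such values. Given the falls needed, I expect the event to be rare, and 20 decisions is a logical ceiling rather than an expectation. No endpoint is affected.

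**What to change.** In Table 2, change the action for a value below 3.8 that has increased to "Continue with current dose, but notify study nephrologist". The dosing action stays as it is, and no other section needs to change. The cost is one phrase, plus in practice at most a few extra messages to a nephrologist who already receives them for other rows.

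As a clarification only, add a footnote that change is measured from the previous weekly value, and from screening for week 1. Other rows depend on this too: with 5.6 at screening, 5.2 at week 1 and 5.4 at week 2, the week 2 value is a decrease from screening (continue) but an increase from the previous week (contact).
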